6.2.6 Dose Escalation Procedure

In Phase I, four sequential INXN-1001 dose escalation cohorts are planned, as described in [Appendix 5](#). Subject enrollment and dose escalation will proceed according to a standard 3+3 design. No intrasubject dose escalation will be allowed. An intermediate dose level(s) of INXN-1001 may be explored after review of all available safety and activity data, as may be decided by the SRC.

Approximately 15 subjects will be enrolled in Phase II at or below the MTD. To increase the ability to estimate the effect of the treatment on clinical response and to correlate with immunologic or other biologic markers, an additional number of subjects may be entered into the study after the initial safety evaluation has been completed.

6.2.7 Study Stopping Rules

Rules for stopping dose escalation due to DLTs observed during the first cycle of study treatment are outlined in [Section 6.2.4](#). In the event that a given dose is determined to have exceeded the MTD, then further use of that dose will be discontinued for all subjects as noted in [Section 6.2.4](#). Subsequent to Cycle 1, study drug-related adverse events that meet the DLT criteria will also be considered by the SRC and any previous determination of the MTD may be reconsidered.

Stopping rules for toxicities that occur from Day 1, Cycle 2 through the Post-treatment follow-up visit will apply as follows:

- If an adverse event can be definitely shown to be unrelated to study treatment (eg, motor vehicle accident, bee sting, elective surgery), that specific toxicity will not be considered in a stop vs. dose modification decision.
- Recruitment in the current dose level will not be stopped for Grade 2 (NCI CTCAE v.4.03) non-dose limiting toxicities, irrespective of the number of events or number of subjects.
- Recruitment in the current dose level will be stopped for any Grade 4 toxicity. Upon occurrence, all data will be reviewed by the Investigator, the Investigator's IRB as applicable, ZIOPHARM Medical and Regulatory Staff, and the SRC to determine if the study should proceed and if/what changes must be implemented.
 - For toxicity based on laboratory tests: an abnormality related to study drug per investigator assessment must be confirmed (when appropriate) by repeat testing before qualifying for review as above.
- Subject enrollment into the study will be halted in the event of any study drug-related death. In this case, subject enrollment will only resume following review and approval of the SRC.

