6.2.3 Safety Review Committee (SRC)

A SRC comprised of the Medical Monitor, Principal Investigators and sponsor representatives, will hold periodic teleconferences to evaluate the safety and treatment status of all subjects. The SRC will review and assess the safety data at the completion of each dose cohort as described in Section 6.2.6, and at any other time as needed. The SRC has the authority to recommend dose modifications for safety concerns.

A written summary documenting the results and recommendations of each review will be provided to the Investigator(s) and maintained on file with the sponsor. Additional sub-Investigators and personnel may participate in reviews as indicated.

In Phase I, following a cohort review, the SRC may recommend proceeding with enrollment in the next dose cohort, enrolling additional subjects in the current cohort, dropping back to a lower cohort, exploring an alternate dose level, or not enrolling any additional subjects. The dose escalation and enrollment guidelines outlined in [Section 6.2.6](#), as well as the study stopping rules outlined in [Section 6.2.7](#), will be used as the basis for these assessments.

In Phase II, Group 2, the DLT definitions in [Section 6.2.4](#) will be utilized along with the criteria for de-escalation. The SRC may recommend a dose reduction for subjects in Group 2 if one or more DLT(s) are observed.

While the SRC is expected to reach a consensus opinion regarding any premature discontinuation or significant modification of the study, the sponsor may independently stop the study.

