6.2.4 Definition and Management of Dose-Limiting Toxicity (DLT)

Dose-limiting toxicity (DLT) is defined as:

- Any injection site reaction that includes ulceration, necrosis, severe tissue damage or where operative intervention is required.
- Any local or systemic injection reaction that has life-threatening consequences, requires urgent intervention or results in death.

- Any study drug-related \geq Grade 3 adverse event, except nausea and/or vomiting in subjects who did not receive optimal treatment with anti-emetics.

Phase I and Phase II, Group 1: If DLTs have been observed in >1 of the 3-6 subjects in a cohort during the first treatment cycle, the MTD will have been exceeded and further use of that dose will be discontinued in all subjects, and the next lower dose cohort will be assessed as to whether it meets the definition of the MTD.

Phase II, Group 2: If an adverse event that meets the Phase I DLT definition is observed in >1 of the 3-6 subjects in Group 2 during the first treatment cycle, the SRC will convene to discuss reduction in dose and/or change to posology and the cohort will be expanded by 3 subjects. The recommended Phase II dose will be the dosage and posology where ≤ 1 of 3 to 6 subjects experiences an adverse event as described in the definition of DLT.

The Medical Monitor should be immediately notified of any potential DLT. Subjects will be withdrawn from study treatment if they experience an injection site reaction that meets DLT criteria or other Grade 3 toxicity related to study drug that, upon review of the SRC, is deemed to be a DLT. If, however, the subject has experienced a substantial benefit from treatment and the SRC recommends continuation on the study, re-exposure to the experimental treatment may proceed at a lower dose of INXN-1001 on a case by case basis. Any subject who experiences a Grade 4 toxicity related to study treatment will be withdrawn from study.

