8.2.7 Severity Grading and Management of Injection Site Reactions

Injection of a biologic agent carries a potential risk of injection site reaction which is characterized as an intense reaction (usually immunologic) at or near the site of injection. Injection reactions will be graded according to the National Cancer Institute (NCI) Common Terminology Criteria for Adverse Events (CTCAE) version 4.03.

[Table 3](#) outlines the injection site reaction grading system, associated symptoms, and the recommended actions to be taken. For any injection reaction, a serum tryptase level will be measured. Reactions at the INXN-2001 injection site that occur within 24 hours after the injection and are attributed to INXN-2001 will be considered to be injection related AEs.

Table 3. Injection Site Reaction Severity Grading and Management

CTCAE Grade	Symptoms	Course of Action
1	Tenderness with or without associated symptoms (eg, warmth, erythema, itching)	No intervention required.
2	Pain; lipodystrophy; edema; phlebitis	Proceed with further dosing cycles.
3	Ulceration or necrosis; severe tissue damage; operative intervention indicated	Discontinue further study treatment and notify Medical Monitor. Report and manage as DLT: see Section 6.2.4 . If toxicity meets seriousness criteria, immediately report as per SAE reporting procedures; see Section 9.4 .
4	Life-threatening consequences; urgent intervention indicated	Permanently discontinue study treatment and notify Medical Monitor. Report and manage as DLT: see Section 6.2.4 . Defaults to “serious”. Immediately report as per SAE reporting procedures; see Section 9.4 .
5	Death	Immediately notify Medical Monitor and report as per SAE reporting procedures; see Section 9.4 . Discontinue further subject enrollment as per study stopping rules; see Section 6.2.7 .

As with all AEs, injection-related signs or symptoms which, in the Investigator's judgment, are not related to immunologic reactions (eg, dyspepsia, urinary frequency, etc) should be recorded and graded as AEs according to NCI CTCAE v.4.03 criteria in the CRF. Study stopping rules will not apply to a specific event if it is clearly unrelated to INXN-2001 injection (eg, accidental trauma). If an AE associated with injection cannot be definitely shown to be unrelated to INXN-2001, then study stopping rules will apply.

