17. APPENDIX 3: SUGGESTED REGIMEN FOR HYDRATION, ANTI PYRETIC AND/OR ANALGESIC PROPHYLAXIS

Recombinant adenoviral vectors have the potential to elicit potent cellular and humoral immune responses in recipients. While the mechanism responsible for these effects is poorly understood, dehydration and transient low-grade fevers are common after systemic recombinant adenovirus vector administration and temperatures up to 104° F with chills and generalized malaise have been observed in first and/or subsequent treatment cycles.

Dehydration may occur in the absence of adequate hydration prophylaxis. Subjects must be instructed to maintain adequate oral hydration on and in between dosing days; sites must closely monitor subjects' hydration status. Oral hydration is of paramount importance after first injection of INXN-2001 through Cycle 2 because most toxicity has been observed during this time period.

Because low grade fever is very likely to occur, prophylaxis with a non-steroidal anti-inflammatory agent (ibuprofen) or acetaminophen (if a subject cannot tolerate ibuprofen) is strongly recommended starting with Cycle 1.

- Ibuprofen is available without a prescription in 200 mg tablets. Usually 800 mg every 6-8 hours will prevent and/or decrease fever. The lowest expected efficacious dose should be used.
 - Side effects of ibuprofen include nausea and vomiting, which may be prevented if the medication is taken with food. Rare side effects include diarrhea, constipation, heartburn, and stomach pain. People with stomach ulcers or kidney disease, and those with an aspirin allergy should avoid ibuprofen.
 - Common brand names of ibuprofen include Advil®, Motrin®, and Nuprin®.
 - Aspirin should be avoided as it may be toxic in large doses in adults.
- While meta-analyses suggest that ibuprofen is a better anti-pyretic medication than acetaminophen, acetaminophen also prevents and or reduces a fever. It is available without a prescription in 325 mg or 500 mg tablets. Again, 1000 mg every 6-8 hours should be used to eliminate fever. The maximum dose of acetaminophen in adults should not exceed 4 grams in a 24 hour period.
 - Side effects are rare, but some people are allergic to the medication. Over doses may cause liver failure. Therefore, people with liver disease and chronic alcohol users should avoid this medication.
 - Common brand names of acetaminophen are Aspirin Free Anacin®, Feverall®, Genapap®, Panadol®, Tempra®, and Tylenol®.

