Dose Escalation Plan During Phase I	
Phase I: Four sequential INXN-1001 dose escalation cohorts are planned, as described in Table 1. Subject enrollment and dose escalation will proceed according to a standard 3+3 design. No intrasubject dose escalation will be allowed. An intermediate dose level(s) of INXN-1001 may be explored after review of all available safety and activity data, as may be decided by the SRC.
 
Initially, 3 subjects will be enrolled into each sequential dose cohort, beginning with the lowest planned INXN-1001 dose level.
 
Dose escalation will not occur until the third subject in a cohort has completed the first treatment cycle (7 days of oral activator ligand followed by 14 days of observation). Following this, a meeting of the SRC will be convened to review all reported \geqGrade 3 adverse events to determine if these meet dose-limiting toxicity (DLT) criteria. In addition, the SRC will review the overall occurrence of adverse events and relevant laboratory data in each cohort to determine whether the MTD has been reached. Following this review, the SRC will advise on subject enrollment, dose escalation and/or cohort expansion using the following guidelines:
 
a) If 0 of 3 subjects in a cohort experiences a DLT, then the next higher dose-level cohort may be enrolled.b) If 1 of 3 subjects in a cohort experiences a DLT, then up to 3 additional subjects will be enrolled into that cohort.c) If >1 of 3-6 subjects in a cohort experience a DLT, then enrollment into that cohort will cease, and the previous dose-level will be explored as the maximum tolerated dose (MTD). A total of 6 subjects will be enrolled into this lower-dose cohort, including previously enrolled subjects. Using the same criteria, lower-dose cohorts will be explored as the MTD until ≤ 1 of 6 subjects experience a DLT.d) Intermediate INXN-1001 dose levels may be recommended by the SRC (i) to advance the INXN-1001 dose in a smaller increment than originally planned, or (ii) to better determine the MTD. The intermediate dose level(s) will not exceed the higher of either a dose level in which >1 of 3 or 6 subjects experienced a DLT or the highest planned dose level (ie, Cohort 4, 160 mg/day). If 160 mg is the MTD and pharmacokinetic data suggests that higher dose(s) of INXN-1001 are indicated, then additional dose cohorts may be explored following an approved amendment of this protocol.
--	--

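### Section 6.2.7 lists the mandatory enrollment halt for a drug-related death under a Cycle 2 lead-in; read literally, one related death in Cycle 1 is a single DLT with no required hold

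*Protocol*

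**What the plan says.** Protocol section 6.2.7 divides treatment time in two. Its opening paragraph sends first-cycle DLTs to section 6.2.4. A second lead-in, "Stopping rules for toxicities that occur from Day 1, Cycle 2 through the Post-treatment follow-up visit will apply as follows", then introduces four rules. The fourth is "Subject enrollment into the study will be halted in the event of any study drug-related death", and enrollment restarts only once the SRC has reviewed the case and agreed.

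Section 6.2.4 includes in its DLT definition "Any local or systemic injection reaction that has life-threatening consequences, requires urgent intervention or results in death", and separately any drug-related event of Grade 3 or above (apart from inadequately treated nausea or vomiting). Any related death is therefore a DLT. In Phase I and Group 1 a dose is abandoned when more than 1 of 3–6 subjects has a first-cycle DLT. In Group 2 the same count obliges the SRC to meet about dose or schedule, and 3 subjects are added.

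For a single DLT, the Phase I guideline (b) in Appendix 5 (Dose Escalation Plan) is "If 1 of 3 subjects in a cohort experiences a DLT, then up to 3 additional subjects will be enrolled into that cohort". For Group 2, section 6.2.3 says "The SRC may recommend a dose reduction for subjects in Group 2 if one or more DLT(s) are observed".

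Section 8.2.7 refers back to the stopping rules twice without naming a cycle. The Grade 5 row of Table 3 says "Discontinue further subject enrollment as per study stopping rules" and points to 6.2.7. The text below the table says "If an AE associated with injection cannot be definitely shown to be unrelated to INXN-2001, then study stopping rules will apply".

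**The concern.** The same event gets two different responses depending on when it happens. A related death from Cycle 2 onward stops accrual until the SRC approves a restart. A related death in Cycle 1, on the literal text, adds one to a DLT count that needs two before anything is compulsory.

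Nothing in the protocol explains why a Cycle 1 death should be handled less strictly. Appendix 3, in explaining why hydration matters from the first injection through Cycle 2, gives the reason "because most toxicity has been observed during this time period", so the uncovered cycle lies inside the period the protocol itself singles out. What is at stake is subject safety: people could start treatment at a dose that has just caused a death before anyone is required to review it. No estimate or analysis is affected.

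**Working it through.** The plan gives no figure to reproduce, so the check is to follow one related death through the rules as written.

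**Inputs.** Section 6.2.7 (time window, halt); section 6.2.4 (DLT definition, threshold); section 6.2.1 and Appendix 5 (stagger, timing of the SRC meeting, guideline (b)); section 6.2.3 (SRC powers); section 8.2.7 with Table 3; SAP sections 1.0 and 6.1 (subjects treated).

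**1. Size of the window.**
- Phase I and Group 1: 21 / (6 × 21) = 21/126 = 16.7% of planned treatment time.
- Group 2: 28 / (6 × 28) = 28/168 = 16.7%.
- Subjects who enter Cycle 1: 13 (Phase I) + 13 (Phase II) = 26 treated. Of these, 4 + 3 + 2 = 9 were on every-other-day regimens (Group 2), the group for enrollment under Amendment 7 or later.

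**2. Related death in Cycle 2 or later.** The halt applies, and no new subject enters until the SRC approves.

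**3. Related death in Cycle 1, injection reaction or injection-associated.** Section 8.2.7 and Table 3 call for the stopping rules, but the section they point to has a lead-in that excludes Cycle 1. The two places contradict each other.

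**4. Related death in Cycle 1, not treated as injection-associated** (for example, attributed to INXN-1001). Section 8.2.7 does not reach it, and only the DLT count remains.
- DLT count = 1. The threshold of more than 1 requires at least 2, so it is not met.
- *Phase I.* Other subjects may start 7 days after the first subject in a cohort, and the planned SRC meeting comes after the third subject finishes the 21-day cycle. If the first subject dies, 2 more can start before that meeting. After it, guideline (b) allows up to 3 more: 2 + 3 = up to 5 further subjects, provided no second DLT occurs, with no compulsory halt along the way.
- *Group 2.* At a count of 1 the SRC has discretion to recommend a lower dose. That is not an enrollment hold.

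| Related death | Response required by the text |
|---|---|
| Cycle 2 onward | Enrollment halted until SRC approval |
| Cycle 1, injection-associated | Contradictory: 8.2.7 and Table 3 stop, 6.2.7 lead-in excludes |
| Cycle 1, other | One DLT; Medical Monitor told; no required hold |

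**The case against.** The best case on the other side is that this is a misplaced bullet whose intent is plain. The halt covers any related death and acts on the whole study, not a dose level, and Table 3 carries no cycle limit. INXN-2001 is injected about 3 hours after the first INXN-1001 dose of each cycle, and INXN-1001 works by switching on the injected gene, so few Cycle 1 deaths could be cleanly separated from the injection.

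There are also several safeguards. The SRC is convened on enrollment questions, can meet whenever needed and in Phase I can advise against enrolling anyone else. The Medical Monitor is told at once of a possible DLT, SAEs are reported within 24 hours, and the sponsor controls registration and can stop the study. Guideline (b) is advice applied after SRC review, not automatic accrual. The Appendix 3 remark is about hydration, does not separate Cycle 1 from Cycle 2, and says nothing about deaths. Only about 9 of the 26 treated subjects fall in the group enrolled under the current amendment.

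Much of this stands. Intent probably was all cycles, the practical risk is reduced, and both the 16.7% and the 26 describe scope, not risk. But every safeguard listed is notification or discretion, and from Cycle 2 the protocol requires more than that. In Phase I, SRC review precedes the extra 3 subjects but not necessarily the second and third. Section 8.2.7 classifies only injection-site reactions within 24 hours, leaving it open how a later systemic death would be classed. No sentence requires a hold for a related Cycle 1 death judged not to be injection-associated.

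**Conclusion.** The concern holds. As written, the compulsory halt for a related death begins at Cycle 2. In Cycle 1 such a death is one DLT against a threshold of two. Where it is not treated as injection-associated, nothing requires a hold; where it is, sections 6.2.7 and 8.2.7 disagree.

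The gap covers Days 1–21 or 1–28, one of six planned cycles, and in Phase I could let up to 5 further subjects enter the dose after a death in the first subject. This rests on reading the lead-in as governing every item beneath it, and on no second DLT occurring. The documents give no rate of related death, so no probability is attached. The rule should be corrected because following it literally gives a less protective result than the protocol evidently meant. The sample size and the planned analyses are unaffected.

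**What to change.** Move the death rule out from under the Cycle 2 lead-in in section 6.2.7, or add one sentence. Suggested wording: from the first dose of study drug, in every phase and cycle, a death assessed as related to study drug halts enrollment until the SRC has reviewed it and approved resumption; this takes precedence over the DLT count in section 6.2.4 and guideline (b) in Appendix 5.

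The Table 3 reference would then point to a rule that covers Cycle 1. The Grade 4 recruitment stop sits under the same lead-in, but Cycle 1 Grade 4 events are already handled through the DLT count. That handling and the recommended Phase II dose rule can stay as they are.

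The cost is one bullet moved or one sentence added, plus a possible short pause in accrual for SRC review. The 3+3 count, sample size and analyses do not change. Because the SAP already reports the treated numbers for the final analysis, the correction matters for any further enrollment under this text and for any later protocol built on it.

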7. SUBJECT SELECTION

The target population for this study is adult subjects with unresectable Stage III or IV melanoma for which there is no alternative curative therapy.

7.1 INCLUSION CRITERIA

To be enrolled in the trial, each subject must satisfy all of the following inclusion criteria:

1. Males or females of all races \geq 18 years of age, who have provided written informed consent prior to completing any study specific procedure.
2. Unresectable Stage III or Stage IV melanoma arising from any site other than ocular melanoma.
3. A minimum of 2 accessible lesions (shortest diameter \geq 1 cm) or palpable tumor-involved lymph nodes (shortest diameter \geq 1.5 cm).

4. ECOG performance status of 0 or 1 ([Appendix 1](#)).
5. Adequate bone marrow, liver, and renal function, as assessed by the following laboratory requirements:
 - a. Hemoglobin \geq 9 g/L
 - b. Lymphocytes $> 700/\text{mm}^3$
 - c. Neutrophils $\geq 1,500/\text{mm}^3$
 - d. Platelets $\geq 100,000/\text{mm}^3$
 - e. Serum creatinine $\leq 1.5 \times \text{ULN}$
 - f. AST and ALT $\leq 2.5 \times \text{ULN}$. For subjects with documented liver metastases, ALT and AST $\leq 5 \times \text{ULN}$
 - g. Total bilirubin $< 1.5 \times \text{ULN}$
 - h. International Normalized Ratio (INR) and activated partial thromboplastin time [PTT] $< 1.5 \times \text{ULN}$, if not therapeutically anticoagulated. Subjects who are being therapeutically anticoagulated with an agent such as Coumadin (warfarin sodium) or subcutaneous heparin may be included provided there is no prior evidence of underlying abnormality in coagulation parameters, screening test results are in appropriate therapeutic range, and anticoagulation regimen is stable and closely monitored.
6. An expected survival of at least 6 months.
7. Male and female subjects must agree to use a highly reliable method of birth control (expected failure rate less than 5% per year) from the screening visit through 28 days after the last dose of study drug.

7.2 EXCLUSION CRITERIA

Subjects will be excluded from enrolling in the trial if they meet any of the following exclusion criteria:

1. Any prior anti-cancer therapy or investigational agent within 28 days prior to the first dose of study drug.

NOTE: For Phase II ONLY, if subjects received ipilimumab, a 45-day washout period since last dose of ipilimumab is required. If subjects received other immunomodulating therapies (eg, anti-PD1 antibodies), the medical monitor should be contacted and an evaluation will be made.

2. Clinically significant infection requiring systemic antibacterial, antifungal, or antiviral therapy within 2 weeks of the first dose of study drug.
3. History of HIV infection.
4. Active autoimmune disease requiring steroids ($> 10 \text{ mg prednisone or comparable}$) or other immunosuppressive therapy (eg, methotrexate, etc.).

5. Documented symptomatic brain metastases. Screening for brain lesions by CT or MRI is not required for all potential subjects; however, if there are any neurological signs or symptoms consistent with brain metastases, then a brain CT or MRI should be performed as clinically indicated.
6. Any medications that induce, inhibit or are substrates of CYP450 3A4 within 7 days prior to the first dose of study drug.
7. Prior history of hematopoietic stem cell transplant or organ allograft.
8. Other concurrent clinically active malignant disease, with the exception of other cancers of the skin.
9. Females who are nursing or pregnant.
10. Subjects who have a history of hypersensitivity that may relate to any component of the study drugs, eg to benzoic acid since INXN-1001 contains two benzene rings.
11. Unstable or clinically significant concurrent medical condition that would, in the opinion of the investigator, jeopardize the safety of a subject and/or their compliance with the protocol. Examples include, but are not limited to, unstable angina, congestive heart failure, recent (within 2 months of screening) myocardial infarction, ongoing maintenance therapy for life-threatening ventricular arrhythmia, uncontrolled asthma, evidence of hepatic pathology due to or consistent with infection with a chronic hepatitis virus, uncontrolled major seizure disorder, or electrolyte imbalances.
12. Local infection at site of injectable lesion requiring anti-infective therapy within 2 weeks of the first dose of study drug.

